PROTOCOL TITLE: INTRANASAL INSULIN FOR IMPROVING COGNITIVE FUNCTION IN MULTIPLE SCLEROSIS

DATE: November 20, 2020

VERSION: 2.4

SYNOPSIS

This will be a randomized, double-blind, placebo-controlled phase I/II pilot study. Participants will be randomized to intranasal insulin 10 international units (IU) twice a day, 20 IU twice a day, or placebo for 24 weeks. Insulin will be administered intranasally using the novel ViaNaseTM controlled particle dispersion system, allowing for direct delivery of the medication to the nasal epithelium, leading to maximal transport to the CNS (Kurve Technology, Lynnwood, WA).³⁴ Cognitive assessments will occur at baseline and throughout the 24-week trial, as well as for a period of 24 weeks after discontinuation of the intervention, to evaluate the impact of insulin on cognitive performance as well as the longevity of the treatment response. Biomarkers of cellular stress, neuronal injury, oxidative stress, inflammation, and energy metabolism will be assessed at baseline and at subsequent visits. Stored specimens will be acquired for more detailed future mechanistic studies if intranasal insulin does appear to be safe and effective.

INTRODUCTION

Cognitive impairment is common in and devastating to people with MS. MS is a common, chronic, central nervous system (CNS) disease characterized by inflammation, demyelination, and neurodegeneration. One of the most devastating symptoms of this disease is impaired cognitive function, which is common and present in over 60% of individuals with MS.¹⁻³ MS-related cognitive impairment is associated with lowered quality of life ⁴ and reduced functional capacity, including loss of employment,⁴⁻⁷ impaired social relationships,⁸ compromised driving safety,⁷ and poor adherence to treatment.⁹ Impaired cognitive functioning has been observed early in the disease, sometimes even before diagnosis,¹⁰ and cognitive function has been shown to decline longitudinally, both over the short- and long-term.¹¹⁻¹³ Several cognitive domains are impacted in people with MS, including attention, memory, executive functioning, and especially processing speed.^{2, 10, 14-18}

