Intranasal Insulin for Cognition in MS is an Innovative Treatment Approach-Summary

Insulin appears to activate biologically relevant pathways within the nervous system for regulating and improving learning and memory. The direct and indirect effects of insulin on energy metabolism, oxidative stress, and modulation of inflammatory and neuronal pathways, along with the data from clinical trials in people with other neurodegenerative disorders, prove the rationale for investigating it in people with MS who suffer with cognitive impairment. As noted above, reduced levels of insulin and/or insulin activity may contribute to a number of pathological processes that may ultimately lead to long-term disability in neurodegenerative diseases. Restoring brain insulin to normal levels and increasing insulin sensitivity in the brain may provide therapeutic benefit to people with MS. Herein, we thus propose the first clinical trial in MS to determine the safety and tolerability as well as the effectiveness of intranasal insulin as a therapeutic intervention for cognitive dysfunction. Our study will investigate associated changes in putative biomarkers (see Preliminary Data below) that may corroborate clinical outcomes and provide data regarding the mechanisms by which insulin acts. These measures, along with neuropsychological testing, will be incorporated with safety data in order to accurately assess the potential utility of intranasal insulin for MS cognitive impairment.

OBJECTIVES/AIMS

Primary Objective: To evaluate the safety and tolerability of intranasal insulin in people with MS

Secondary Objectives: The main secondary objective is to evaluate if intranasal insulin improves cognition in people with MS, as assessed by the SDMT. Additional secondary objectives are to determine if intranasal insulin is associated with changes in additional components of the Minimal Assessment of Cognitive Function in MS (MACFIMS), the Multiple Sclerosis Functional Composite (MSFC) score, health-related quality of life

(Functional Assessment of Multiple Sclerosis [FAMS]), the Expanded Disability Status Scale (EDSS) score, and changes in biomarkers of oxidative stress, neuronal injury, cellular stress, and metabolism.

Aim 1. To evaluate the safety and tolerability of intranasal insulin in people with MS.

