Exploratory Biomarkers Plasma and/or PBMCs will be collected at baseline, week 12, and week 24 visits (except if COVID-19 related shutdown does not permit follow-up blood collection or lab-based processing) and will be isolated and cryopreserved for batch analyses in the labs of [name] or [name]. Inflammatory (cytokines, lymphocyte subsets), metabolic (Kreb's cycle substrate, fatty acids), cellular stress (ceramides, sphingomyelin) and neurotrophic (BDNF) measures, as well as markers of oxidative stress (protein carbonyls, 8-isoprostane, nitrotyrosine, and 4-hydroxynonenal adducts [lysine and histidine]), will be quantified. Since our data show oxidative stress biomarkers and elevated ceramides in plasma of MS patients and recent work shows

the brain has lymphatics, explaining how brain metabolites return to the periphery, blood biomarkers are a relevant and convenient way to monitor CNS metabolism.⁶²

Additional Outcomes and Assessment of Covariates In order to identify and, if needed, adjust for comorbid depression, the Beck Depression Inventory will be administered at each study visit. Health-related quality of life will also be assessed utilizing the FAMS. We will also evaluate how overall sleep quality in people with MS impacts health-related quality of life. We will also evaluate for occult insulin resistance or differences in metabolism in several ways. We will evaluate dual-energy x-ray absorptiometry (DXA) at baseline, which will help determine body composition, in particular bone density. We will also calculate an insulin resistance index, the homeostatic model assessment (HOMA-IR),⁶³ using baseline fasting glucose and insulin. Statistical models exploring these body composition and insulin resistance parameters as potential confounders or mediators will be evaluated. Finally, the MACFIMS, safety, depression, and health-related quality of life outcomes will be monitored after discontinuation of the insulin (or placebo) to evaluate for any decline in cognitive function associated with medication discontinuation.

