Safety/Adverse Event Monitoring An adverse event (AE) is any occurrence or worsening of an undesirable or unintended sign, symptom (or abnormal laboratory test), or disease temporally associated with the use of a medicinal product or intervention, whether or not it is considered related to the product/intervention. We will use the National Cancer Institute's Common Terminology Criteria for Adverse Events version 4.0 to report and grade all adverse events, whether or not they are related to disease progression or treatment. The relationship between an AE and the intervention will be determined by the blinded study physician and recorded on the appropriate form. The investigator will record all study adverse events in the chart and will treat participants with AEs appropriately, observing them until they resolve or stabilize. AEs will be collected from the start of the study until a participant terminates from the study; those that are unresolved at the time of termination will be followed until they resolve or up to 30 days. An adverse event is considered unexpected when its nature or severity is not consistent with the product information (e.g. protocol or the informed consent form). Serious AEs will be collected from informed consent signing until 30 days after study completion or until 30 days after a participant withdraws from the study. The following process for reporting a serious AE will ensure compliance with the International Conference on Harmonisation guidelines: the Institutional Review Board (IRB) and DSMB will be notified in two business days of a serious AE that is medication-related and unexpected, and standard reporting (15 calendar days) will occur if the event is serious, expected and medication-related, serious, expected and not medication-related, or serious, unexpected and not medicationrelated. Life-threatening events will be reported within 7 calendar days. Any pregnancy will be reported to the IRB and DSMB, and pregnancies will be followed to their conclusion. Female participants who become pregnant will stop the study intervention. The investigator will report pregnancies to the IRB within two business days. The study medication will be discontinued if an AE grade 3 or higher occurs and is at least possibly related to the medication or if the subject cannot tolerate the medication/ wants to discontinue it. Any death that is at least possibly related to the study will put the study on hold until the DSMB evaluates it.

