Aim 1. Safety data will be analyzed as they are captured in real time. Assessments will focus on AEs (including study treatment tolerability assessments, laboratory evaluations, vital signs, and physical examination). The incidence rate of AEs will be recorded by system organ class, severity, and by relationship to the study treatment. Tolerability analysis will be based on the number (%) of subjects who failed to complete the study due to adverse events. Lab values for each parameter will be summarized by shift tables. For quantitative parameters, summary statistics for actual values and change from baseline will be presented. Changes in the first 24 weeks will be compared between groups using mixed effects regression analyses to account for the longitudinal nature of the data using random subject-specific intercepts and slopes.

Aim 2. Summary statistics (mean ± standard deviation, median and interquartile range, or number and percentages) will be used to characterize the outcomes. For each cognitive outcome, to evaluate variability in the estimated means across groups, assuming that the within-group means are normally distributed, a one-way ANOVA will be conducted at the follow-up visits during the first 24 weeks. If the within-group data are strongly non-Gaussian, a Kruskal-Wallis test will be used. A mixed effects longitudinal model will also be used to test whether any differences across groups exist at the follow-up visits within the first 24 weeks. Further, models accounting for covariates of interest, including the HOMA-IR, body composition, body mass index, age, sex and depression, will be used. For within-person changes in measures at follow-up compared to baseline, paired t-tests will be used. We will also evaluate the SDMT at each study visit and other MACFIMS outcomes at week48 to establish the longevity of any therapeutic response to insulin.

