Aim 3. For the biomarker outcomes, to evaluate variability in the estimated means across groups, assuming that the within-group means are normally distributed, a one-way ANOVA will be conducted at the follow-up visits during the active treatment phase. If the within-group data are strongly non-Gaussian, a Kruskal-Wallis test will be used. A mixed effects longitudinal model will also be used to test if differences across groups exist at follow-up visits. For within-person changes in measures at follow-up compared to baseline or before versus after calorie restriction days, paired t-tests will be used. Correlations between the biomarkers will be assessed. A bootstrap of subjects will be used to obtain 95% equal confidence intervals for these measures. We will also evaluate the biomarker changes after study therapy ends.

Sample Size and Power: Sample size estimates are difficult given the novelty of the project but are based on the goal of detecting a benefit of insulin on cognition. In a pivotal study of two doses of intranasal insulin versus placebo in participants with mild cognitive impairment or mild to moderate Alzheimer's Disease, the Dementia Severity Rating Scale score improved over the four-month treatment course in those receiving intranasal insulin.³⁴ Using the scores in the 10 IU twice a day group, given a two-sided alpha of 0.05 and beta 0.20 (80% power), assuming 3 follow-up cognitive tests and a correlation between baseline and follow-up results of 0.5, 29 subjects per group are required. To account for drop-outs and for the three-arm design, a total of 35 subjects per group is planned. With SDMT as the outcome, for a two-arm design, this sample size confers 80% power (assuming SDMT standard deviation of 9 points and two-sided alpha of 0.05) to detect a 6-point improvement in SDMT which seems reasonable considering that transcranial stimulation with cognitive training

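### Tolerability is counted as failing to complete the 48-week study because of AEs, not as stopping study drug, so it can miss participants who stop drug and stay, and count some who finished dosing

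*Protocol*

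**What the plan says.** The primary objective in the protocol's Objectives/Aims is "To evaluate the safety and tolerability of intranasal insulin in people with MS". The only tolerability measure that the Analytic Plan defines for it, under Aim 1, is this: "Tolerability analysis will be based on the number (%) of subjects who failed to complete the study due to adverse events".

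The Safety/Adverse Event Monitoring section deals with stopping of drug in its own sentence: "The study medication will be discontinued if an AE grade 3 or higher occurs and is at least possibly related to the medication". That sentence goes on to give two further grounds, intolerance and the participant's own wish to stop. Leaving the study appears elsewhere in that section as a different event. For example, "AEs will be collected from the start of the study until a participant terminates from the study".

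The Synopsis sets 24 weeks of treatment and continues cognitive assessment "as well as for a period of 24 weeks after discontinuation of the intervention", so completing the study means reaching week 48. On numbers, "a total of 35 subjects per group is planned", with two insulin groups and one placebo group.

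The available SAP text (section IV) lists adverse events as a secondary outcome, with counts by arm. It lists no outcome for stopping drug.

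**The concern.** Intolerance of a drug shows itself when someone stops taking it. The stated measure instead records whether someone left the study. The two can come apart in both directions:

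- **Missed.** A participant stops insulin in week 3 because of nasal irritation, keeps attending, and reaches week 48. This person completed the study and is not counted.
- **Counted.** A participant takes all 24 weeks of drug and leaves at week 40 because of an AE, 16 weeks after the last dose. This person did not complete the study and is counted.

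The measure would also improve as the site got better at retaining people who had stopped drug, which has nothing to do with how well the drug is tolerated. At stake is the one summary figure that most directly addresses the tolerability half of the primary objective.

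**Working it through.** The plan gives no rate, threshold or power for tolerability, so there is no figure to reproduce. The check compares definitions, followed by an illustration.

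**Step 1. Are stopping drug and leaving the study the same event in this protocol?** The safety monitoring section names the reasons for stopping medication and does not add that the participant then leaves. AE collection ends at termination from the study, not at the last dose. The Independent Research Monitor may remove a person from the study, which is a separate power again. SAP section VIII bases eligibility for the primary analysis on having a baseline or screening SDMT, not on continued dosing. The documents therefore treat the events as distinct and leave open what happens after an early stop.

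**Step 2. Which period does the measure cover?** The study lasts 24 + 24 = 48 weeks, of which (48 − 24)/48 = 50% is off drug in every arm. Aim 1 limits its between-group comparison of changes in quantitative parameters to the first 24 weeks but gives the tolerability count no such limit.

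**Step 3. How far can the count move?** Let

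- N = 70 insulin participants (2 × 35, from Sample Size and Power);
- q = share who stop drug for an AE (assumed; not in the documents);
- s = share of those who nevertheless complete the study (assumed; not in the documents);
- L = number who complete dosing and then leave in weeks 24 to 48 for an AE (unknown).

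The number who stop drug for an AE is N × q. The number that the stated measure counts is N × q × (1 − s) + L. With L = 0, the expected counts out of 70 are:

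| q | Stop drug for an AE | s = 0 | s = 25% | s = 50% | s = 75% | s = 100% |
|---|---|---|---|---|---|---|
| 5% | 3.5 | 3.5 | 2.6 | 1.75 | 0.9 | 0 |
| 10% | 7 | 7 | 5.25 | 3.5 | 1.75 | 0 |
| 20% | 14 | 14 | 10.5 | 7 | 3.5 | 0 |

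At q = 10%, the reported rate runs from 7/70 = 10% (s = 0) to 0/70 = 0% (s = 100%). The exact (Clopper-Pearson) 95% intervals at those ends are 4.1 to 19.5% and 0 to 5.1%. In a single arm of 35, if 7 stopped and all stayed, the measure would read 0/35 (0 to 10.0%) where the proportion stopping is 7/35 = 20% (8.4 to 36.9%).

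At s = 0 the two definitions agree for the treatment period. L does not depend on s, so the off-drug miscount remains possible even then.

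**The case against.** The strongest reply is that the undercount depends on something the documents do not state. A reader might infer that the protocol keeps every early stopper in follow-up to week 48, which would make the undercount certain. The text does not support this. The remark under Additional Outcomes about monitoring after insulin or placebo ends most naturally describes the planned observation phase, and the visit tables do not address early stoppers. If in practice everyone who stops drug for an AE also leaves the study for it, there is no undercount. This part of the objection stands and limits the finding to what the wording allows.

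The second reply is that the information is not lost. Aim 1 also tabulates AE incidence by organ class, grade and attributed relation to treatment, and mentions tolerability assessments without defining them. The DSMB meets for any AE of grade 3 or higher. This is true and lowers the severity, but those tables do not show how many people stopped drug.

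The third reply is that little formal inference rests on the count: it carries no test, threshold or power, and the SAP makes SDMT change primary and adverse events secondary. This also stands. It would be wrong to conclude that the safety assessment as a whole is unsound.

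Nor are all late withdrawals irrelevant to tolerability, since an AE that begins on drug can persist past week 24. Finally, the SAP text before section III was not available for this review, so it cannot be said that the SAP as a whole lacks a definition.

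**Conclusion.** The concern holds as a defect of definition. Taken literally, the tolerability measure does not count a participant who stops drug for an AE and remains in the study, and does count one who completes dosing and leaves in weeks 24 to 48 for an AE.

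The size cannot be fixed from the documents. On an assumed 10% stopping rate among 70 insulin participants, the undercount lies between none and all 7, depending wholly on the unknown share who stay. The number of late leavers is equally unknown.

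This should be fixed, because the figure serves the protocol's primary objective and the repair is simple. It is not critical, because AE tables accompany the count and no formal decision depends on it.

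**What to change.** In Aim 1, define tolerability as the number (%) of participants who permanently stop study drug because of an AE or because they cannot tolerate it, between first dose and the end of the 24-week treatment period. Report it by arm and for pooled insulin versus placebo, with exact confidence intervals. Report AE-related study non-completion separately, as participant disposition. Carry the same definition into the SAP's safety outcomes. This alters only what is counted and leaves the rules for stopping treatment untouched.

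The cost is small but not nil. The reported rate may look less favourable. The new count also needs the date of and reason for stopping drug. The documents describe medication review, return of unused drug and AE recording, but do not say that these two items are captured. Check the case report form first, and add the items if they are absent.

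### Aim 3 biomarkers: the planned between-arm ANOVA leaves out the baseline value already collected, and the paired t-tests have no placebo comparison

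*Protocol*

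**What the plan says.** Protocol, Analytic Plan, Aim 3 lists three analyses for the biomarkers.

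- **Follow-up values between arms:** "a one-way ANOVA will be conducted at the follow-up visits during the active treatment phase", or a Kruskal-Wallis test if the data are far from normal. No baseline term is mentioned.
- **A longitudinal model:** "A mixed effects longitudinal model will also be used to test if differences across groups exist at follow-up visits". The text does not say whether baseline is an outcome, a covariate or absent.
- **Change from baseline:** "For within-person changes in measures at follow-up compared to baseline or before versus after calorie restriction days, paired t-tests will be used". No comparison with placebo is attached. The reference to calorie restriction does not belong to this trial, so the sentence needs editing in any case.

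Nothing says which of the three carries the inference. Baseline biomarkers are collected in the standard visit schedule, in the COVID-19 schedule and in the Exploratory Biomarkers text. Randomisation is stratified by relapsing versus progressive MS (Protocol, Study Treatment).

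Aim 2 (cognition) has the same structure: "a one-way ANOVA will be conducted at the follow-up visits during the first 24 weeks", then "A mixed effects longitudinal model will also be used to test whether any differences across groups exist at the follow-up visits", then "For within-person changes in measures at follow-up compared to baseline, paired t-tests will be used". Its covariate list ("models accounting for covariates of interest, including the HOMA-IR, body composition, body mass index, age, sex and depression, will be used") does not include the baseline value of the outcome.

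The SAP differs. Section VIII analyses SDMT and the other cognitive tests by a linear mixed model over weeks 0, 6, 12 and 24. The treatment-by-time term is the quantity of interest, and any insulin versus placebo is the first test. Neither the outcome list in Section IV nor the models in Sections VIII and IX include a biomarker. The part of the SAP before Section III was not available, so this describes the visible text only.

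**The concern.** A between-arm test on follow-up values alone carries all the stable person-to-person variation in its error term, and any chance baseline imbalance passes into the estimate. The baseline sample would remove much of both at no extra cost.

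A paired t-test within one arm answers a different question: whether the arm's mean moved. Drift in an assay or any other trend common to all arms can make it significant, in the placebo arm as well. If its p-values are read as evidence about insulin, the randomised control is discarded.

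Aim 3 has a stated hypothesis that insulin improves these markers, and the protocol makes a power statement for ceramides. The choice of test therefore has some weight even in an exploratory aim.

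**Working it through.** **Inputs from the protocol (Sample Size and Power):** 35 per arm, two-arm comparison, two-sided alpha 0.05, 80% power; SDMT SD 9 and difference 6; ceramide difference 10 ng/mL. A baseline/follow-up correlation of 0.5 is given, but for the dementia-scale calculation. For ceramides and SDMT it is an assumption, so a range is shown.

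**Step 1. Reproduce the plan's own figure.** The detectable difference is (1.960 + 0.842) × SD × √(2/n). For SDMT this is 2.802 × 9 × √(2/35) = 6.03 points. Power for 6 points is 0.796 by the normal approximation and 0.785 by the noncentral t. The stated 80% reproduces, using the plain SD with no correlation factor. That fits an unadjusted follow-up comparison, although a change score has the same SD when r = 0.5.

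The ceramide figure cannot be reproduced because no SD is given. Working backwards, 10 / (2.802 × √(2/35)) = 10 / 0.670, an implied SD of about 14.9 ng/mL.

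**Step 2. Effect of baseline adjustment.** With one follow-up value, the residual variance after adjustment is SD² × (1 − r²), so the detectable difference is multiplied by √(1 − r²). A between-arm comparison of simple change scores multiplies it by √(2(1 − r)). Starting from 10 ng/mL, taken as unadjusted:

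| Assumed r | Variance removed (r²) | Equivalent extra patients, 1/(1 − r²) − 1 | ANCOVA, ng/mL | Change score, ng/mL |
|---|---|---|---|---|
| 0.3 | 9% | 10% | 10 × √0.91 = 9.5 | 10 × √1.4 = 11.8 |
| 0.5 | 25% | 33% | 10 × √0.75 = 8.7 | 10 × √1.0 = 10.0 |
| 0.7 | 49% | 96% | 10 × √0.51 = 7.1 | 10 × √0.6 = 7.7 |
| 0.8 | 64% | 178% | 10 × √0.36 = 6.0 | 10 × √0.4 = 6.3 |

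The last column shows why the handling of baseline has to be stated. Comparing changes gains nothing at r = 0.5 and loses at r = 0.3, while covariate adjustment does better than both alternatives at every r shown.

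**Step 3. The paired t-test with no drug effect.** Suppose every arm drifts by δ SDs. The noncentrality is δ√n / √(2(1 − r)), with n = 35. The drift sizes below are assumptions; the documents give none for biomarkers.

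| Shared drift | r = 0.5 | r = 0.8 |
|---|---|---|
| 0.22 SD (2/9) | 25% | 52% |
| 0.33 SD (3/9) | 48% | 86% |

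These are the chances that a given arm, placebo included, shows a significant within-arm change although insulin does nothing.

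**The case against.** The case against is strong in several places.

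- A reader might infer that change is tested only within arms. The documents do not support that. Both aims also plan a between-group mixed model, which is close to the remedy. What stands is that the Aim 3 model leaves the role of baseline open and is not named as the governing analysis.
- A reader might extend the criticism to the SDMT and the other cognitive tests. The SAP mixed model answers it there: baseline is among the visits, and the test is insulin versus placebo on change. No ANOVA or paired t-test appears in the visible SAP.
- A reader might attribute spurious within-arm change to practice effects and to enrolling people with low scores. Those mechanisms belong to cognition. Eligibility selects on SDMT or PST, not on biomarkers, and blood markers have no practice effect. For Aim 3 only the general point holds: a common time trend cannot be told from a drug effect.
- A reader might conclude that the ANOVA is wrong. Under randomisation it is valid and unbiased; the loss is precision only. The protocol's SDMT power target is met without adjustment.
- The paired t-tests are described as addressing within-person change, and nothing says they will support a claim about insulin. That is fair, but nothing rules it out either.
- Aim 3 is declared exploratory, in a pilot that does not expect conclusive evidence of efficacy for cognition. This lowers the severity.

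**Conclusion.** The point holds for Aim 3 as a free improvement of low severity. The stated between-arm test ignores a baseline that is collected anyway, the paired tests are uncontrolled, and the visible SAP does not settle how biomarkers will be analysed.

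The size depends on the correlation. The detectable ceramide difference would fall from 10 to between 9.5 ng/mL (r = 0.3) and 6.0 ng/mL (r = 0.8), with 8.7 at r = 0.5. This rests on two assumptions: that the protocol's 10 ng/mL refers to an unadjusted comparison, and that r lies in this range for ceramides. The documents confirm neither. The paired-test rates illustrate what an assumed drift would do and do not predict one.

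For Aim 2, what remains is a difference of wording between protocol and SAP.

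**What to change.** **Aim 3.** Replace the one-way ANOVA with a between-arm ANCOVA, or a mixed model, on the follow-up value. Include as covariates the baseline value of the same biomarker and the randomisation stratum (relapsing/progressive). Use a log or rank scale if the data are clearly non-normal, in place of Kruskal-Wallis. Name this model as the inferential analysis. Report within-arm change as mean and 95% CI without p-values, and delete the reference to calorie restriction days. Put the biomarker analysis in the SAP if it is not in the part that was unavailable.

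**Aim 2.** Align the protocol text with the SAP mixed model, and treat any within-arm change as descriptive.

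**Cost.** Analysis wording only. Baseline biomarkers and MS subtype are already collected, and no visit, sample or patient is added.
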